## **ii. Safety**

The secondary safety objectives of the study are:

- Determine the rate of post-surgical wound complications after pre-operative radiation and capecitabine
- Determine the rate of grade III toxicities (excluding acute skin toxicity)

## **iii. Translational endpoint:**

The biomarker research objectives of the study are:

- To determine if change in the absolute number of circulating tumor cells (CTCs) in the blood during pre-operative radiation with or without chemotherapy correlates to the percentage of viable cells in a tumor core biopsy expressing putative stem/progenitor cell markers pre and post therapy. Patients whose gross disease cannot be completely encompassed by a combination of locoregional therapy with chemo/HOU/UTMDACCiation and surgery will be analyzed separately.

The Time and Events Table is included in Appendix E.

# **11.0 Power Calculations and Statistical Analysis**

## **11.0 Power Calculations & Statistical Analysis**

### **11.1 Hypotheses**

The primary objective of this study is to determine response rate after completion of all protocol specified neoadjuvant chemotherapy+ concurrent radiation. The regimen will be considered of interest for further study if the response rate is at least 80% and the grade III toxicity excluding acute skin toxicity is <20%.

### **11.2 Treatment Comparisons**

As all eligible patients will receive the same treatment, there will be no comparisons between treatments.

### **11.3 Sample Size Considerations and Interim Analyses**

The primary objective of this study is to determine the efficacy of pre-operative radiation with concurrent capecitabine in patients who have experienced a minimal response or progression after standard neoadjuvant chemotherapy. Efficacy will be determined by tumour response (complete response + partial response) as measured by RECIST criteria. Tumour response will be assessed after 45 Gy. Those who do not finish will be considered non-responders. Toxicity will be assessed at the same time. Surgical complications will be assessed independently within 6 weeks of surgery. Only grade three toxicity will be considered in the stopping rules. This study will be monitored for both efficacy and safety. Safety will be determined by the rate of grade 3 or higher toxicities, excluding acute skin toxicity. This regimen will not be considered of interest for further study if there is a high probability that the response rate is less than 80% or the severe toxicity rate is greater than 20%. Priors regarding response are based on combined retrospective data from three studies of 135 total patients treated for gross disease in the breast at our institution and detailed in the background (sections 3.2 and 3.5). Local control (a surrogate for response) at 5-years in patients treated for gross IBC disease in the breast with radiation alone was 75% (N = 42, unpublished). In 38 similar patients with non-inflammatory breast cancer local control was 70% at 5 years. In an unpublished retrospective analysis of 55 patients treated with the regimen proposed herein, 5-year local control was 85% (Perkins, SABCS abstract, 2007). There are limited and poor data regarding radiation alone toxicity in this exact cohort. The priors for toxicity were based on aggressive xrt in post-mastectomy patients (N = 192). In these patients, we expect a 15% rate of Grade 3 toxicities in patients receiving 60Gy and a 29% rate of Grade 3 toxicities in patients receiving 66Gy, and unpublished data. Clinically we are currently limiting the use of the latter regimen based on the impression that this is unacceptably high toxicity, so we are targeting a Grade 3 toxicity rate of no more than 20%. All patients who receive any treatment will be included in the analyses of both efficacy and safety. Patients who are not evaluable for response will be considered non-responders. The final analysis will be an Intent to Treat analysis. A total of 60 patients will be enrolled at the rate of 3-4 patients per month. Stopping boundaries will be assessed in cohorts of 5 patients after a minimum of 10 patients have been enrolled. Response and toxicity will be monitored independently. The method of Thall and Simon will be employed to perform interim monitoring.

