## 4.0 Protocol Specified Treatment

### 4.1 Dose Rationale for Concurrent Capecitabine and Radiation

[figure not shown]
Protocol participation is such that the treatment will be administered as an outpatient. Inpatient status is not required and change in status does not necessitate removal from protocol. Based on concurrent capecitabine radiation data in non-breast sites reviewed above as well as from our preliminary experienced reviewed retrospectively in pre-operative concurrent breast cancer, the dosage administered to each patient will be 825 mg/m^2 bid. One of the two daily doses of capecitabine should be taken approximately 2 hours before receiving radiotherapy. The first day of Capecitabine is the the same day that radiotherapy is started and the last day that Capecitabine is given is the last day of radiotherapy. Capecitabine will be administered only on the days the patient receives radiation therapy.

Doses for capecitabine will be calculated on the basis of milligrams of drug per square meter of body surface area (BSA) as measured at baseline (mg/m^2). The weight of the patient may change throughout the study, however, body surface area will be assumed to stay close to that measured at baseline and therefore will be the basis for all dose calculations during the study participation by the patient. The calculation will be performed using the UTMDACC clinicportal BSA calculator. Once this value is obtained the result will be in mg/m^2 and then will be rounded to the nearest number of whole 500 and 150 mg tablets so that two daily oral doses are given. The doses should be separated by 12 hours and are to be taken within 30 minutes after ingestion of food. The tablets should not be manually divided as they are not scored.

Protocol based radiation therapy dose will be 50-57 Gy to the initial clinical target volume (CTV, gross disease + tissue at risk for micrometastatic disease including margin around gross disease and draining regional lymphatics). Additional "boost" dose to bring the total dose to 60-72 Gy to gross target volumes (GTV) defined by the presence of gross disease on pre-treatment imaging is acceptable but not mandated by the protocol.

Optional Preoperative/definitive regimens include:  
Any palliative regimen <3 Gy per fraction is allowable

1. 50-54 Gy at 2 Gy per fraction (one daily treatment) followed by optional GTV boost at 2 Gy per fraction to total dose;

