Linear accelerator based CT imaging (CT on rails or cone beam CT) or re-CT-simulation will be performed after 45 Gy to assess for the need to re-plan secondary to response. Tumor size will be documented using recist criteria based on these images. Additional accelerator based CT imaging is acceptable as clinically indicated.

Definitive or palliative local therapy with surgery when indicated will be performed after completion of the combined regimens. If the patient is deemed operable the first follow-up visit will occur after surgery. If the patient is deemed inoperable the first follow-up visit will occur after concurrent Capecitabine and radiation therapy. Subjects will be followed every 3 months (+/- 1 month) post treatment times 1, then every 6 months (+/- 1 months) times 1, then every 12 months (+/- 2 month) times 2. PET/CT scan or ultrasound will be performed in conjunction with the first follow up visit. For patients treated to definitive dose for gross unresected disease (any treatment field receiving a total of > 60 Gy in the mosaic prescription), all sites receiving > 60 Gy will be scored as complete response, partial response, noresponse/progressive disease based on imaging and exam after this visit and when evaluable and all subsequent visits. Subsequent radiologic studies will be at the discretion of the treating oncologist as dictated by standard of care. Toxicity will be recorded at each visit using the RTOG criteria.

Capecitabine dose reduction criteria are as follows:

Capecitabine will be held for patients experiencing grade 3-4 Capecitabine related

toxicities until symptomatic improvement (Grade 1). Radiation therapy will not be held for Capecitabine related toxicities. Patients will then be restarted with reduced dose of Capecitabine (level-1). Level -1 (25% dose reduction) = 600 mg/m^2 BID. If patients develop additional grade 3-4 toxicity in spite of dose reduction, the chemotherapy will be permanently discontinued.

Correlation will be made between Change in CTC level and change in percent of CD44+CD24lo or ALDH1+ cells in the tumor biopsy. Change will be correlated with clinical and pathologic response (in patients who undergo surgery)

Approximately 60 subjects will be enrolled. Assuming an average accrual rate of 3-4 subjects per month, the duration of accrual will be approximately 20 to 26 months.

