
### 11.3.1 Efficacy and Safety Monitoring

$R,E$  is the probability of response with the study regimen and its assumed prior distribution is  $\text{beta}(1.6, 0.4)$ .  $R,S$  is the targeted response rate and its assumed prior distribution is  $\text{beta}(80, 20)$ . The trial will be stopped early if  $\text{Pr}[R,E < R,S \mid \text{data}] > 0.95$ .  $T,E$  is the probability of severe toxicity from the study regimen and  $T,S$  is the targeted rate of severe toxicity. The assumed prior distribution of  $T,E$  is  $\text{beta}(0.4, 1.6)$  and the assumed prior distribution of  $T,S$  is  $\text{beta}(20, 80)$ . The trial will be stopped early if  $\text{Pr}[T,E > T,S \mid \text{data}] > 0.925$ .

The stopping boundaries corresponding to above probability criteria are:

Number of Patients Evaluated	Number of Responses <=	Number of Toxicities >=
10	5	5
15	8	6
20	12	8
25	15	9
30	19	11
35	22	12
40	26	13
45	30	15
50	33	16
55	37	17
60	40	19

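### Section 11.3 times the toxicity behind the stopping rule at the 45 Gy assessment, before any listed preoperative/definitive course is finished, and no available text brings later events into the boundary counts

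*Combined protocol and SAP*

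**What the plan says.** Section 11.3 gives the timing in two nearby sentences: "Tumour response will be assessed after 45 Gy" and "Toxicity will be assessed at the same time". It sets a separate window for surgical events only: "Surgical complications will be assessed independently within 6 weeks of surgery". The toxicity that counts is grade 3 or higher, excluding acute skin toxicity.

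The same section explains the 20% limit by dose: "we expect a 15% rate of Grade 3 toxicities in patients receiving 60Gy and a 29% rate" at 66 Gy, the latter regarded as too high. Section 11.3.1 defines T,E as "the probability of severe toxicity from the study regimen" and tabulates boundaries at 10, 15, ..., 60 patients evaluated.

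On treatment, section 4.1 lists three preoperative/definitive regimens: 50-54 Gy, 57 Gy, and 51 Gy twice daily. A boost to a total of 60-72 Gy to gross target volumes "defined by the presence of gross disease on pre-treatment imaging is acceptable but not mandated by the protocol". For capecitabine, "the last day that Capecitabine is given is the last day of radiotherapy". Section 6.0 says that CT imaging "will be performed after 45 Gy to assess for the need to re-plan secondary to response", and also that RTOG toxicity is recorded at every visit. Section 11.6.1 evaluates response 4 weeks after radiation ends.

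**The concern.** For every listed preoperative/definitive regimen, 45 Gy falls during treatment. Section 6.0 treats it that way, because imaging done to decide on re-planning is useful only while fractions remain. A toxicity count taken then omits the last part of the base course, any sequential boost, the last capecitabine doses and the weeks after treatment. It is nevertheless compared with a limit argued from 60 and 66 Gy.

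The mismatch works in one direction: a regimen that is too toxic is stopped less often, or later. This is a patient-safety rule in a trial that allows up to 72 Gy with concurrent capecitabine, so the event window should be explicit.

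**Working it through.** **Inputs.** Toxicity boundaries from section 11.3.1: stop at 5, 6, 8, 9, 11, 12, 13, 15, 16, 17 or more toxicities at 10, 15, ..., 55 patients. The look at 60 is not early. True toxicity is 0.30 and response 0.95, a row of the section 11.3.3 table. At 95% response, stopping for low response is negligible and is ignored.

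**Reproducing the plan.** The posterior rule Pr[T,E > T,S | data] > 0.925, with priors beta(0.4, 1.6) and beta(20, 80), returns all eleven toxicity boundaries. An exact binomial recursion (add five patients, remove the paths at or above the boundary, repeat) gives stopping probabilities 0.003, 0.12 and 0.63 at toxicity 0.10, 0.20 and 0.30. Average sizes are 59.8, 55.4 and 38.0. All match the published rows.

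**How far through treatment 45 Gy is.** 45/50 = 0.90, 45/51 = 0.88, 45/54 = 0.83, 45/57 = 0.79. With a sequential boost, 45/60 = 0.75 and 45/72 = 0.63. Dose share is not event share, so these are for scale only.

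**Assumed share s of counted events present by 45 Gy:** 0.90, 0.75, 0.50. The documents give no figure.

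**How long events stay unseen.** Delay = remaining treatment days after 45 Gy / 5, plus 4 weeks to the section 11.6.1 evaluation:

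- 51 Gy bid: 6/1.5 = 4 fractions = 2 days; 0.4 + 4 = 4.4 weeks
- 50 Gy: 5/2 = 2.5 days; 4.5 weeks
- 54 Gy: 9/2 = 4.5 days; 4.9 weeks
- 57 Gy: 12/1.8 = 6.7 days; 5.3 weeks
- 60 Gy: 15/2 = 7.5 days; 5.5 weeks
- 72 Gy at 2 Gy daily: 27/2 = 13.5 days; 6.7 weeks

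At 3-4 patients per month (52/12 = 4.33 weeks), 4.4 x 3/4.33 = 3.0 and 6.7 x 4/4.33 = 6.2. So about 3-6 patients are incomplete at a look.

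**Updated counts.** At the look at n, the first n - L patients are counted in full, and the newest L contribute only events present by 45 Gy, with L = 3 to 6 (simulation of 400,000 trials; L = 5 also by exact recursion).

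**Frozen counts.** Each patient contributes only events present by 45 Gy, at every look. The counted rate is 0.30 x s = 0.27, 0.225 or 0.15.

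| Early-stopping probability (published 0.63) | s = 90% | s = 75% | s = 50% |
|---|---|---|---|
| Updated, L = 3 to 6 | 0.61 to 0.60 | 0.60 to 0.56 | 0.56 to 0.50 |
| Frozen at 45 Gy (worst case) | 0.45 | 0.22 | 0.03 |

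Average sizes, against 38.0, are 39.2, 41.1 and 44.3 with updated counts at L = 5, and 44.2, 52.2 and 58.8 with frozen counts.

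**Final judgement.** Below 20% of 60 means at most 11 (11/60 = 18.3%). The probability of finishing with at most 11 is 0.03 under the published design. It stays at 0.03 with updated looks and a complete final count. It becomes 0.08, 0.27 or 0.81 only if looks and final count are both frozen at 45 Gy.

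**The case against.** The strongest reply is that the 45 Gy cut-off is inferred. Section 11.3 sets a start and no closing time, whereas section 6.0 states upper limits where it wants them, as for the surgical consultation and the second biopsy. Toxicity is recorded at each visit, T,E refers to the whole regimen, and section 11.5 analyses safety in all treated patients without a dose limit. Section 11.6.1 puts response 4 weeks after radiation, so the underlying fault may be the conflict over response timing, which toxicity merely inherits. The Time and Events Table (Appendix E) is not in the text available and might say more.

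Much of this stands. A reader might infer that counts are frozen at 45 Gy and known later events ignored; no text says so. A reader might also infer that the operating characteristics are wrong. They are correct for whatever toxicity endpoint is counted; what is in doubt is whether that endpoint matches the 60 and 66 Gy benchmark. Palliative courses have no stated total dose, so 45 Gy need not fall mid-course for them.

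It does not remove the point. If the wording means any time after 45 Gy, the count at each look has no defined end. If it means the 45 Gy imaging, the count is truncated. Either way the text needs the same edit.

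**Conclusion.** The point holds, with a modest likely effect. Taken literally, section 11.3 feeds the boundaries an on-treatment count and compares it with a full-course limit. If later events are picked up at subsequent looks, stopping at 30% toxicity falls from 0.63 to no lower than about 0.50 under the assumed shares, and to about 0.60-0.61 if 90% of events are present by 45 Gy. The large losses (0.45, 0.22, 0.03) need frozen counts and are a bound, not an expectation. A reader might also infer that the final judgement against 20% is compromised. The documents do not support that, since nothing limits the final count to 45 Gy. All sizes rest on assumed shares and on the accrual rate in the plan. The change is worth making because the rule protects patients and the edit is small.

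**What to change.** In section 11.3, replace the sentence "Toxicity will be assessed at the same time" with:

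> For the 11.3.1 boundaries and the <20% criterion in 11.1, a toxicity is any grade 3 or higher RTOG toxicity, excluding acute skin toxicity and surgical complications (assessed separately), from first dose through the evaluation 4 weeks after radiation (11.6.1). Counts are cumulative and updated at every look; the look at n is complete when the first n patients have reached that evaluation or left the study, and the trial stops at once if they reach the boundary sooner.

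The boundary table and stopping probabilities do not change.

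Costs: each look completes about 4.4-6.7 weeks later than one taken at 45 Gy, so about 3-6 more patients may be enrolled by then. For a too-toxic regimen, average enrolment can exceed the published 38.0 by about 0.63 x 3 = 1.9 to 0.63 x 6 = 3.8, i.e. 2-4 patients. That is similar to the averages with updated counts and a five-patient lag at shares of 90% and 75% (39.2 and 41.1), so at those shares the gain is a defined and complete count more than fewer patients treated. Patients awaiting surgery need toxicity noted at the 4-week evaluation, because their first follow-up visit comes after the operation. The documents do not say whether the 15% and 29% rates include late effects, so a 4-week window may still not match them exactly.

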#### ii. Safety

The secondary safety objectives of the study are:

- Determine the rate of post-surgical wound complications after pre-operative radiation and capecitabine among patients who undergo surgery
- Determine the rate of grade III toxicities (excluding acute skin toxicity)

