##### **11.6.1 Primary Analysis**

The primary endpoint in this study is response defined as the percentage of subjects achieving a complete or partial tumor response using RECIST criteria. The response rate will be calculated from the view of best response that records confirmed cases of CR or PR. Subjects with unknown or missing response will be treated as non-responders; i.e., they will be included in the denominator when calculating the percentage. Response will be evaluated by the recist criteria 4 weeks (+/- 4 days) after completion of radiation therapy.

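### The toxicity stopping rule carries two grade definitions, and the available text does not say whether toxicity after the 45 Gy assessment counts toward it

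*Combined protocol and SAP*

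**What the plan says.** **Grade.** Section 11.3 limits what the boundary counts: "Only grade three toxicity will be considered in the stopping rules". Two sentences later it defines safety: "Safety will be determined by the rate of grade 3 or higher toxicities, excluding acute skin toxicity". Section 1.0 (ii. Safety) and Section 10.0 (ii. Safety) both have "Determine the rate of grade III toxicities (excluding acute skin toxicity". Section 11.1 makes further interest conditional on a rate described as "the grade III toxicity excluding acute skin toxicity is <20" per cent. Section 11.3.1 defines the monitored quantity T,E as "the probability of severe toxicity from the study regimen" and names no grade. Section 6.0 has a rule for capecitabine-related toxicity of grades 3-4, so grade 4 events are foreseen.

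**Timing.** Section 11.3 says "Tumour response will be assessed after 45 Gy" and continues "Those who do not finish will be considered non-responders. Toxicity will be assessed at the same time". Surgical complications are assessed separately. Section 6.0 uses imaging after 45 Gy to decide on re-planning and asks for the surgical consultation between 45 Gy and the last fraction. Section 4.1 gives 50-57 Gy to the initial target volume, with an optional boost to a total of 60-72 Gy. Section 11.1 speaks of response once all protocol therapy is complete, and 11.6.1 says "Response will be evaluated by the recist criteria 4 weeks (+/- 4 days) after completion of radiation therapy". Section 6.0 also has toxicity recorded at every visit.

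**The concern.** The toxicity boundary is the trial's safety stopping rule, so the event it counts has to be unambiguous. Two teams following 11.3 could count differently: one would leave out a grade 4 or 5 event, the other would include it. The same wording reaches the 11.1 criterion for taking the regimen further.

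The timing raises a similar question. T,E is toxicity from the regimen, but the one assessment point that 11.3 ties to toxicity can fall while radiation is still being given. The available text does not say whether an event recorded later is added to the count.

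The operating characteristics in 11.3.3 are correct for whatever event is counted. If that event is narrower than all qualifying toxicity of the full regimen, the trial is less likely to stop at a given true rate than the table suggests.

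**Working it through.** **1. The plan's own boundary.** Inputs from 11.3 and 11.3.1: T,E prior beta(0.4, 1.6); T,S prior beta(20, 80); cutoff 0.925; looks every 5 patients from 10; maximum 60. With k toxicities in n patients, the boundary is the smallest k for which

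Pr[Beta(0.4 + k, 1.6 + n − k) > Beta(20, 80)] > 0.925.

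- n = 10: k = 4 gives 0.884 and k = 5 gives 0.963, so the boundary is 5 (printed 5).
- n = 30: k = 10 gives 0.920 and k = 11 gives 0.959, so the boundary is 11 (printed 11).
- n = 60: k = 18 gives 0.919 and k = 19 gives 0.947, so the boundary is 19 (printed 19).

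All eleven printed toxicity boundaries reproduce. They depend only on priors, cutoff and counts, not on how an event is defined.

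**2. The plan's own operating characteristics.** I ran an exact binomial recursion on the toxicity boundary alone, with stopping possible at n = 10, 15, ..., 55. The 11.3.3 rows with 95% response are the right comparison, because the response boundary hardly ever acts there.

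| True toxicity | Early stop, computed | Printed | Average N, computed | Printed |
|---|---|---|---|---|
| 10% | 0.0035 | 0.003 | 59.8 | 59.8 |
| 20% | 0.122 | 0.12 | 55.4 | 55.4 |
| 30% | 0.626 | 0.63 | 38.0 | 38.0 |

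**3. What under-counting would do (illustration).** Let s be the share of qualifying events that reach the count. The documents give no value, so s is assumed. Counted rate = 0.30 × s.

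| s | Counted rate | Early stop | Average N |
|---|---|---|---|
| 1.00 | 0.300 | 0.63 | 38.0 |
| 0.95 | 0.285 | 0.54 | 41.1 |
| 0.90 | 0.270 | 0.45 | 44.2 |
| 0.80 | 0.240 | 0.29 | 49.9 |

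**4. How much treatment follows 45 Gy.** (50 − 45)/50 = 10%; (51 − 45)/51 = 12%; (54 − 45)/54 = 17%; (57 − 45)/57 = 21%. With a boost, (60 − 45)/60 = 25% and (72 − 45)/72 = 37.5%. These are shares of dose. They are not shares of events and do not estimate s.

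**5. Effect of the counting convention.** I simulated accrual at 3-4 patients per month, with an assumed toxicity window of 2.0-2.4 months from first dose and uniform onset of events. If events and non-events both enter when the window closes, early stopping at true rates of 15%, 20% and 30% is about 0.03, 0.12 and 0.62, in line with 11.3.3. If events enter at onset while non-events wait for the window to close, it is about 0.05-0.08, 0.19-0.24 and 0.72-0.77. The boundary then stops more readily than 11.3.3 states.

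**The case against.** **Grade.** The paragraph that says only grade three also supplies the wider definition. It then frames its 20% limit as a severe toxicity rate, which is the term 11.3.1 uses for T,E. The narrow sentence follows directly on the one that sets surgical complications apart, and it reads naturally as a floor. This is persuasive about intent. It does not remove the conflict, because the sentence that names the stopping rules is the narrow one and three other places repeat grade III. A reader might infer that the trial means to disregard grade 4-5 events. The documents do not support that: they foresee grade 4 and define safety as grade 3 or higher.

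**Timing.** Assessment after 45 Gy has no upper limit. The clause on patients who do not finish suggests outcomes are settled once completion is known. Sections 11.1 and 11.6.1 put response after treatment, and toxicity is recorded at every visit. Appendix E, the natural place for assessment times, was not in the text available. All of this stands. A reader might infer that toxicity after 45 Gy goes uncollected or is certainly excluded from the count; neither follows. Nor do the 60 Gy and 66 Gy rates cited in 11.3 prove a mismatch, since their time window is not given.

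**Enrolled and evaluated.** Section 11.3 starts the looks after 10 patients are enrolled, while the 11.3.1 table counts patients evaluated. The table heading can fairly be taken to govern the count, so this is no separate contradiction. What is missing is when a patient becomes evaluated for toxicity.

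**Size.** The capture shares are hypothetical and tied neither to grade 4-5 frequency nor to late onset. That stands too.

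**Conclusion.** The grade conflict is firm. Section 11.3 gives two definitions of the event behind the safety stopping rule, and on the literal one grade 4-5 events fall outside both the boundary and the 11.1 criterion. The likely intent is grade 3 as a floor, so this is a wording defect in a rule that would give a wrong count if applied as written. It should be fixed.

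The timing point is secondary and held with moderate confidence, subject to Appendix E. The assessment linked to toxicity can precede the end of radiation in every listed pre-operative or definitive regimen, and the available text does not say whether later toxicities are counted.

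The size is unknown. The fall from 0.63 to 0.54 or 0.45 at a true 30% rate assumes that 5% or 10% of qualifying events are missed. If grade 4-5 events are counted and toxicity is assessed at or after the end of treatment, the loss may be small or nil. A reader might infer that the boundary or the 11.3.3 table is miscalculated. Both reproduce; only the definition of the event is in question.

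**What to change.** 1. **One grade definition.** Reword the stopping-rule sentence in 11.3 to say that only toxicity of grade 3 or higher, acute skin toxicity excepted, counts. Use the same definition in Section 1.0 (ii. Safety), Section 10.0 (ii. Safety), 11.1 and the definition of T,E in 11.3.1.
2. **One toxicity window.** Reconcile 11.3 with 11.6.1 by stating that the boundary counts qualifying toxicities through at least the end of protocol radiation, for example to the four-week evaluation in 11.6.1. Keep surgical complications separate, and align Appendix E if needed.
3. **When a patient is evaluated.** State when a patient enters the evaluated count for toxicity. If events are to be counted before a patient's window closes while non-events wait, recheck the operating characteristics in 11.3.3.

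The printed boundary numbers stay as they are. The cost is mainly wording. If the four-week point is used, a toxicity recording point may have to be added, and each patient becomes evaluable later than at 45 Gy. With 2-7 treatment days left, five treatment days a week (assumed) and four weeks ± 4 days, the delay is 2/5 + 24/7 = 3.8 to 7/5 + 32/7 = 6.0 weeks, and longer with a sequential boost. At 3-4 patients per month (about 4.3 weeks), that is roughly 3 to 6 further enrolments before a look if accrual continues. A window closing at the end of radiation would shorten this but leave out toxicity that appears afterwards.
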